7.2 Medical, Surgical and Cosmetic Procedure History

Medical, surgical, and cosmetic procedural history data will be coded using the Medical Dictionary for Regulatory Activities (MedDRA). The actual version of the MedDRA will be noted in the statistical tables/listings and clinical study report.

All medical, surgical, and cosmetic procedural history data will be listed for the Safety Population.

7.3 Prior and Concomitant Medications

A prior medication is defined as any medication started before the date of first study treatment.

A concomitant medication is defined as any medication taken on or after the date of first treatment.

Prior and concomitant medications will be coded using the World Health Organization Drug Dictionary (WHO DD). The actual version of the WHO DD will be noted in the statistical tables/listings and clinical study report.

All prior and concomitant medications will be listed for the Safety Population.

7.4 Concomitant Procedures

All concomitant procedures will be listed for the Safety Population.

8.0 Efficacy Analyses

8.1 General Considerations

- All efficacy analyses will be conducted in the Evaluable Population.
- Day 1 is defined as the day on which the study treatment is first received.
- Baseline for efficacy is defined as the last non-missing assessment on or prior to Day 1.
- Study day is relative to Day 1.
- Change from baseline will be computed as post-baseline minus baseline.

- Categorical variables will be summarized descriptively using number of subjects with observed values or events (n) and the percentage of subjects with observed values or events.
- Continuous variables will be summarized descriptively using number of subjects with observed values (n), mean, standard deviation (SD), standard error of mean (SEM), median, minimum (min), and maximum (max).
- Unless otherwise specified, the estimated mean and median for a set of values will be printed out to 1 more significant digit than the original values; the SD and SEM will be printed out to 2 more significant digits than the original values; the min and max will report the same significant digits as the original values.
- Shapiro-Wilks test will be used to check the normality assumption. If the normality assumption is met, the statistical hypothesis test will be performed based on one-sample, one-sided t-test at 0.025 significance level. If the normality assumption is not met, Wilcoxon signed-rank test will be used instead and a 97.5% confidence interval (CI) for the median will be presented using the Hodges Lehmann method. Shapiro-Wilks and Wilcoxon signed-rank test will be performed by proc univariate procedure, and Hodges Lehmann CI of the median for paired samples will be performed based on a SAS macro by Han (2008) [\[1\]](#) as specified in SPP Section 3.3.
- All CIs will be 1-sided 97.5% CIs, and will be printed to 2 decimal places, unless stated otherwise. P-values output will be in the format: ‘0.xxxx’, where xxxx is the value rounded to 4 decimal places. Every p-value less than 0.0001 will be presented as <0.0001. If the p-value is returned as >0.9999, then present it as it is.
- Unless otherwise specified, the summaries will be provided by treatment group, gender, and overall.

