 BMI > 30 is exclusionary. Body weight will be measured at screening and end of study (V7) for all subjects. Drastic weight loss or gain may skew assessments of "before" and "after" photos.

 Required for women of childbearing potential

 Pregnancy test not required at V6 if no BOTOX touch-up is needed.

 New subject diary only administered at touch-up if injection occurred. Collect completed diary at the next scheduled visit.

 FACE-Q Scales include Satisfaction with Facial Appearance Scale, Expectations Scale (baseline only), Aging Appraisal, Psychological Function Scale, Social Function Scale, and Satisfaction with Skin Questionnaire.

 FACE-Q Expectations subscale will not be collected at End of Study.

 If HArmonyCa injections are not to be administered to a subject, the subject will begin at Day 1 with V3 study activities (i.e., Juvéderm fillers).

 HArmonyCa touch-up, if required. If not required, proceed with V3 study activities.

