2.2 Study Design Overview

This Phase 4 study is a prospective, interventional, multicenter, combination medical device and drug post marketing study. Each subject will be in the study for up to approximately 5 months and act as his/her own control. All products will be used as per their license only. The investigators will perform all treatments and evaluations.

The study is planned to enroll 60 subjects consecutively at approximately 7 study sites in Brazil. Recruitment will also target men, who are typically under-represented in aesthetic studies.

All subjects will sign an informed consent form (ICF) and begin the study at the screening visit (V0). Subjects following screening (V0) will enter the study and receive an initial treatment of HArmonyCa Lidocaine at Visit 1 (V1), followed by Juvéderm fillers at Visit 3 (V3), and BOTOX at Visit 5 (V5) as indicated in the study design diagram ([Figure 1](#)). If the decision is made to not treat with HArmonyCa Lidocaine, the subject may begin with Juvéderm fillers at V1. As indicated in the diagram, touch-ups of HArmonyCa at Visit 2 (V2), Juvéderm at Visit 5 (V5), and BOTOX at Visit 6 (V6) are optional. If a touch-up of HArmonyCa (V2) is not performed, the subject may advance in the study timeline to the next study visit procedures. If a touch-up of BOTOX is not performed, the subject will return on schedule for Visit 7 (V7). A

subject not receiving Juvéderm touch-up would continue with BOTOX treatment (and all study procedures) outlined for V5. To reduce the number of subject visits, V0 can be combined with the initial treatment visit (V1), if judged by the investigator to be appropriate and acceptable for the subject. End of study is the last clinical visit an enrolled subject has in this study, V7 (after approximately 5 months of treatment). Subjects who discontinue prematurely will be asked to return for the last clinical visit for end-of-study data collection. Identical study procedures will not be repeated where the visits are combined. The schedule of activities is shown in [Table 1](#).

Figure 1. Study Design

[figure not shown]

Table 2. Schedule of Activities (SOA)

Study Visit	V0 ¹	V1	V2	V3	V4	V5	V6 ²	V7 ³
Visit window	Screening	Day 1	Day 30	Day 60	Day 90	Day 120	Day 135	Day 150
	(Day -14 to Day -1)	N/A	(30 ± 7 days after V1)	(30 ± 7 days after V2)	(30 ± 7 days after V3)	(30 ± 7 days after V4)	(15 ± 7 days after V5)	(15 ± 7 days after V6)
STUDY TREATMENTS								

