4.1.2 Evaluable Population

The Evaluable Population is defined as all subjects in the mITT Population who received study products (JUVÉDERM and BOTOX) as treatments in this study, had at least one efficacy assessment at the final visit (V7), and had no significant protocol violations or deviations that will affect any efficacy endpoint. Such significant protocol violations or deviations will be determined during data review.

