4.1.3 Safety Population

The Safety Population is defined as all subjects who received any product as treatment in this study.

Unless otherwise specified, all efficacy analyses will be based on the Evaluable Population. The mITT Population will be used for demographics and baseline characteristics summary. The Safety Population will be used for the protocol deviation and violation, treatment exposure, all safety analyses, and listings unless otherwise specified.

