Appendix C. Changes to Protocol-planned Analyses

Protocol Planned Analysis	Modified Analysis
All efficacy analyses will be based on the mITT and Evaluable Populations.	All efficacy analyses will be based on the Evaluable Populations.
Subgroup analysis by gender and treatment touch-ups.	Subgroup analysis by gender only.
mITT (modified Intent-to-Treat) Population - all subjects who enrolled and had at least one post-baseline efficacy assessment.	mITT (modified Intent-to-Treat) Population - all subjects who enrolled and had at least one post-baseline efficacy assessment at V7.
Evaluable Population– all subjects as defined in the mITT Population who have received both study products as treatments in this study, had at efficacy assessment at the final visit (V7) and no major protocol violations or deviations.	Evaluable Population– all subjects as defined in the mITT Population who have received both study products as treatments in this study, had at efficacy assessment at the final visit (V7) and no major protocol violations or deviations that will affect any efficacy endpoint.
Exploratory efficacy analysis may be performed on the collected video and photographs.	Removed.

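### The SAP drops the protocol's mITT efficacy analysis and tests the primary endpoint only in the Evaluable Population, so some collected V7 scores enter no efficacy estimate

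*SAP*

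**What the plan says.** **Protocol.** Section 11.1.1 assigns efficacy to the mITT Population and adds the Evaluable Population for key efficacy endpoints. Section 11.4 bases efficacy on both unless stated otherwise. The synopsis lets the SAP specify differently, and 11.8 routes changes to planned analyses through a SAP amendment.

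**SAP.** Section 8.1 states: "All efficacy analyses will be conducted in the Evaluable Population". Section 4.1.3 agrees: "Unless otherwise specified, all efficacy analyses will be based on the Evaluable Population". Section 8.3.3 names the Evaluable Population for the primary test, and 8.3.4 marks additional primary analyses as not applicable. Appendix C records the change ("All efficacy analyses will be based on the Evaluable Populations") without a reason.

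**Who is Evaluable.** SAP 4.1.2 starts from mITT, which under 4.1.1 already requires an efficacy assessment at V7. It then keeps subjects "who received study products (JUVÉDERM and BOTOX) as treatments in this study" who also "had no significant protocol violations or deviations that will affect any efficacy endpoint". On timing it says: "Such significant protocol violations or deviations will be determined during data review".

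**V7 data after early discontinuation.** Protocol 6.2.6 and 11.1 ask subjects who stop early to attend the final visit. Section 8.2 asks sites to make every effort to obtain the primary FACE-Q from them.

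**The concern.** Both extra conditions for Evaluable status depend on what happens after baseline. A subject who stops before BOTOX, attends V7 as asked and completes the primary questionnaire is in mITT but in no planned efficacy estimate. The same holds for a V7 attender removed for a deviation. Because the deviation rule refers to any efficacy endpoint, a deviation that matters only for a secondary measure can take a subject out of the primary test.

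The study is open-label with one arm, so the mean change is the finding itself. If excluded subjects changed by a different amount from those retained, the reported mean differs from the mean of everyone assessed, and no planned analysis would show it. The baseline tables (SAP 7.1) stay on mITT, so they may describe a different group from the one that produces the primary result.

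**Working it through.** **1. The plan's own figure.** Inputs from Protocol 11.7 and SAP 2.4: mean change 12.0, SD 25.0, one-sample t-test, 1-sided alpha 0.025, 90% power, 20% drop-out.

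- Noncentrality at n = 48: (12/25) × √48 = 3.33 on 47 degrees of freedom, giving power 0.903. The smallest n with at least 90% power is 48.
- Enrolment: 48 / (1 − 0.20) = 60.

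The sample size reproduces, and nothing here changes it. The drop-out allowance covers early withdrawal and incomplete end-of-study FACE-Q. It does not mention exclusion for a deviation or for a product not received.

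**2. The two populations compared.**

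| Condition | mITT (SAP 4.1.1) | Evaluable (SAP 4.1.2) |
|---|---|---|
| Enrolled | yes | yes |
| Efficacy assessment at V7 | yes | yes |
| Received JUVÉDERM and BOTOX | no | yes |
| No significant deviation affecting any efficacy endpoint | no | yes |
| Efficacy use in the protocol | yes | yes |
| Efficacy use in the SAP | none | all |

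The sets differ only in the third and fourth conditions.

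**3. When the product condition can fail.** BOTOX is first given at V5, nominal Day 120 of 150. It comes earlier if HArmonyCa is not used ("If HArmonyCa injections are not to be administered to a subject, the subject will begin at Day 1 with V3 study activities", Protocol Table 6.1, footnote 13) or if its touch-up is skipped (footnote 14). V3 to V5 is two 30-day intervals, so first BOTOX falls at about Day 60 or Day 90 in those cases. Every path leaves weeks in which a subject can stop before BOTOX and still be asked to attend V7.

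**4. Where these subjects still appear.** They are in the population counts (SAP 5.0) and the significant-deviation summaries and listings (Appendix A). If treated, they are also in the Safety Population FACE-Q listing (8.3.3). None of these is an estimate or a test.

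**5. Size of the possible difference.** Let *f* be the share of V7-assessed subjects excluded and *m* their mean change. Then

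Evaluable mean − mean of all assessed = *f* × (retained mean − *m*).

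The documents give neither *f* nor *m*, and do not say which population the planned mean of 12 describes. Two readings follow:

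- A, 12 is the retained mean: difference = *f*(12 − *m*).
- B, 12 is the mean of all assessed: retained mean = (12 − *fm*)/(1 − *f*), so difference = *f*(12 − *m*)/(1 − *f*).

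All values of *f* and *m* below are assumptions.

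| *f* | *m* | Reading A | Reading B |
|---|---|---|---|
| 0.10 | 6 | 0.10 × 6 = 0.60 | 0.60/0.90 = 0.67 |
| 0.20 | 0 | 0.20 × 12 = 2.40 | 2.40/0.80 = 3.00 |
| 0.10 | 12 | 0 | 0 |
| 0.10 | 18 | 0.10 × (−6) = −0.60 | −0.60/0.90 = −0.67 |

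For scale, the planned standard error at n = 48 is 25/√48 = 3.61 points.

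**The case against.** The change is open and allowed. The protocol lets the SAP specify otherwise, and Appendix C sets the old and new text side by side. There is no randomised comparison for an intention-to-treat analysis to protect. The hypothesis concerns subjects who received the combination, so requiring the products fits the question. The SAP also narrowed the deviation rule: the protocol's Evaluable set excluded any major deviation, whereas the SAP excludes only those affecting an efficacy endpoint, which brings Evaluable closer to mITT. Appendix A has significant deviations identified before database lock. All subjects are intended to receive all treatments, so the excluded group may be small. Restoring mITT would not recover anyone without a V7 score. No illustrated case overturns the conclusion: the lowest all-assessed mean in the table is 12 − 2.4 = 9.6.

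Much of this stands. This is a disclosed choice, its effect is not demonstrated, and mITT does not remove every form of post-baseline selection. But permission and disclosure do not show that the result is robust to the choice. The combination hypothesis supports reporting Evaluable. It does not justify dropping mITT, and it does not cover the deviation filter. Nor does Evaluable match the hypothesis exactly, since the hypothesis names HArmonyCa and Evaluable does not require it. Identification before lock is not the same as identification without sight of V7 scores, which neither 4.1.2 nor Appendix A promises. Selection can shift a single-arm mean even though there is no comparison to protect.

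**Conclusion.** The concern holds and should be fixed. The textual facts are certain: the protocol planned efficacy in two populations, the SAP uses one, and no planned analysis puts V7 attenders who fail an Evaluable condition into an estimate or test. The test remains valid for Evaluable subjects. What the plan cannot show is whether the primary result depends on who was excluded after baseline.

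The documents fix neither the sign nor the size of the effect. The illustrated range of −0.67 to 3.0 points rests on assumed exclusions of 10% to 20% and assumed excluded means of 0 to 18, and it includes zero. All of these gaps are smaller than one planned standard error. No claim about power is made, because that would depend on which population the mean of 12 describes. Part of any difference may reflect a different target population (subjects who received the combination) and not error, which is a reason to report both estimates.

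**What to change.** Restore an mITT analysis of the primary endpoint: all enrolled subjects with baseline and V7 FACE-Q Satisfaction with Facial Appearance scores, regardless of products received or deviations. Report it beside the Evaluable analysis, using the same test and interval. State in SAP 8.3.3 which of the two carries the primary conclusion, and give the reason there and in Appendix C.

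Two optional refinements would strengthen the Evaluable analysis. For the primary test, exclude only for deviations that affect the primary endpoint. State also that exclusions are settled without sight of V7 scores.

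The cost is SAP text and one extra set of primary-endpoint tables, with no new data. The sponsor accepts that the mITT estimate may be less favourable than the Evaluable one.

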8.2 Handling of Missing Data

For all FACE-Q™ questionnaires, the sum of the items will be calculated and converted into an overall score (also known as the Rasch-transformed score) ranging from 0 (worst) to 100 (best). If the number of missing items (which includes selection of more than 1 response for an item, a response of non-applicable (N/A) or skipping a question) is at most 50% of all the items, then insert the unrounded mean of the completed items into the total sum score. Inversely, if the

number of missing items is more than 50%, then the overall score will be missing. The total score will not be calculated in this case and the particular visit will be excluded from the Rasch-transformed score calculation and summary.

For PAAQ questionnaire, all items will be transformed to a scale from 0 (no negative impact) to 100 (high negative impact). Domain scores will be calculated as the average of transformed scale scores using the 50% rule given below:

If the domain has at least 50% non-missing item responses it will be scored as the average of the non-missing responses (with reverse scoring and rescaling as appropriate). If the domain is missing more than 50% of item responses, then the domain score will be set to missing.

For all other questionnaires as specified below, no imputation will be performed.

- Self-Perception of Age Questionnaire
- Global Aesthetic Improvement Scale

8.3 Primary Efficacy Endpoint and Analyses

8.3.1 Primary Efficacy Endpoint

The primary efficacy endpoint is the change from baseline in the overall Rasch-transformed score of the FACE-QTM: Satisfaction with Facial Appearance Scale to the final study visit (V7).

8.3.2 Handling of Missing Data for the Primary Efficacy Endpoint

For the FACE-QTM: Satisfaction with Facial Appearance questionnaire, if the number of missing items (which includes selection of more than 1 response for an item, a response of non-applicable (N/A) or skipping a question) is at most 50% of all the items (i.e., at least 5 items have been answered), then insert the unrounded mean of the completed items into the total sum score. Inversely, if the number of missing items is more than 50% (i.e., less than 5 items have been answered), then the overall score will be missing. The total score will not be calculated in this case and the particular visit will be excluded from the Rasch-transformed score calculation and summary.

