### 8.2 Early Discontinuation of Individual Subjects

A subject may voluntarily withdraw from the study at any time. Notification of early subject discontinuation from the study and the reason for discontinuation will be made to the sponsor and will be clearly documented on the appropriate eCRF. In the event of subject discontinuation, every effort should be made to have the subject complete the primary endpoint FACE-Q Satisfaction with Facial Appearance Overall questionnaire.

It is the right and responsibility of the investigator to discontinue a subject's participation when the subject's health or well-being is threatened by continuation in the study. In the event of premature discontinuation, the investigator should determine the primary reason for discontinuation.

A subject who is withdrawn from the study prior to initiation of treatment may be replaced. Discontinued subjects will not be replaced.

The following are circumstances that could result in a subject's discontinuation from the study:

- AEs or SAEs that render the subject unable to continue study participation
- Protocol violation
- Subject voluntarily withdraws consent
- Non-compliance with study requirements
- Discretion of investigator (must document reason on eCRF)
- Progressive injury (at the discretion of the investigator)
- Changes in the subject's condition that render the subject unacceptable for further participation, in the judgment of the investigator
- Pregnancy (required discontinuation)
- Lost to follow-up
- Unable to physically or mentally tolerate the use of the test treatment
- Exclusion criterion met

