### 11.4.3 Missing Data

The missing data strategy will be documented in the SAP.

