2.0 Study Design and Objectives

2.1 Objectives and Hypotheses

The primary objective of this study is to quantify the psychological, social, and emotional impact of comprehensive aesthetic treatment with a portfolio of AbbVie's products by measuring the change in subject's satisfaction with facial appearance from baseline to the final study visit

(Statistical Programming Plan [SPP] Appendix C FACE-QTM: Satisfaction with Facial Appearance). These products include BOTOX, HArmonyCa Lidocaine, and Juvéderm facial fillers, as described in [Section 1.0](#) and [Section 2.3](#).

The secondary objectives are:

- To determine the subject's self-appraisal of aging appraisal (SPP Appendix D FACE-QTM: Aging Appraisal), psychological function (SPP Appendix E FACE-QTM: Psychological Function), social function (SPP Appendix F FACE-QTM: Social Function) and satisfaction with skin (SPP Appendix G FACE-QTM: Satisfaction with Skin).
- To quantify the investigator's and subject's assessment of aesthetic improvement.

The clinical hypothesis of this study is that subjects treated with a combination of BOTOX, HArmonyCa Lidocaine facial filler, and Juvéderm facial fillers will be satisfied with their overall facial appearance at the final study visit as measured by the change from baseline on the FACE-QTM Satisfaction with Facial Appearance Overall Scale.

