2.3 Treatment Assignment and Blinding

Approximately 60 subjects will be enrolled consecutively at approximately 7 study sites in Brazil. Recruitment will also target men, who are typically under-represented in aesthetic studies. Study treatments include:

- **BOTOX:** The dose and the number of injection points may be adapted to the needs of the subject, based on their characteristics and location of the muscles to be treated. Subjects will receive at least one BOTOX treatment in the following areas: glabellar lines (GLs), crow's feet lines (CFLs), and forehead lines (FHLs).
- **HArmonyCa Lidocaine:** The investigator will determine the appropriate volume to be injected during initial and touch-up treatments based on his/her clinical experience. The maximum total volume of HArmonyCa Lidocaine allowed per subject for the initial and touch-up treatment combined is 4 syringes (5 milliliter [mL]).
- **JUVÉDERM:** The investigator will determine the appropriate volume to be injected during initial and touch-up treatments based on his/her clinical experience.
 - JUVÉDERM VOLITE [REDACTED]: The maximum total volume of JUVÉDERM VOLITE [REDACTED] allowed per subject for the initial and touch-up treatments combined is 4 syringes (4 mL).
 - JUVÉDERM VOLBELLA with Lidocaine: The maximum combined total volume of JUVÉDERM VOLBELLA with Lidocaine allowed per subject for all facial areas treated for both the initial and touch-up treatments combined is 2 syringes (2 mL).
 - JUVÉDERM VOLIFT with Lidocaine: The maximum total volume of JUVÉDERM VOLIFT with Lidocaine allowed per subject for the initial and touch-up treatments combined is 4 syringes (4 mL).
 - JUVÉDERM VOLUMA with Lidocaine: The maximum total volume of JUVÉDERM VOLUMA with Lidocaine allowed per subject for the initial and touch-up treatments combined is 4 syringes (4 mL).

- JUVÉDERM VOLUX with Lidocaine: The maximum total volume of JUVÉDERM VOLUX with Lidocaine allowed per subject for the initial and touch-up treatments combined is 4 syringes (4 mL).

The investigator should not inject greater than 20 mL of filler (Juvéderm and HArmonyCa Lidocaine) per 60 kg (130 lbs.) body mass per year for a single subject.

Blinding and randomization are not applicable. This is an open-label, single-arm study. Subjects are enrolled consecutively based upon subject need and all subjects are intended to receive all treatments. Investigators will perform all treatments and evaluations.

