2.4 Sample Size Determination

A sample size of 48 subjects will provide 90% power to detect if change from baseline to end of study visit in the FACE-Q™: Satisfaction with Facial Appearance Overall Scale Rasch-transformed score is different from zero, assuming a mean change of 12.0 and a standard deviation of 25.0.

This calculation is based on a one-sample, 1-sided t-test at 0.025 significance level. The assumptions of mean and standard deviation are based on FACE-Q™ results from the HARMONY Study GMA-CMB-14-001. Anticipating a potential 20% drop-out rate (for early withdrawals and/or subjects who failed to duly complete the FACE-Q™: Satisfaction with Facial Appearance Overall Scale assessment at end of study), 60 subjects will be enrolled.

PASS 2008 software was used to calculate the sample size.

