4.0 Analysis Populations and Subgroup

4.1 Analysis Populations

4.1.1 Modified Intent-to-Treat (mITT) Population

The mITT Population is defined as all subjects who enrolled and had at least one post-baseline efficacy assessment at V7.

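### The primary mean change is computed only from Evaluable subjects with a V7 FACE-Q score, and the SAP neither handles an absent V7 score nor plans a supportive analysis to bound its effect

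*SAP*

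**What the plan says.** Protocol 11.4.3 gives no method of its own: "The missing data strategy will be documented in the SAP".

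The SAP's answer is in sections 8.2 and 8.3.2, and it stays at the level of items. If at most half of the FACE-Q items are missing, the mean of the answered items is used. If more are missing, there is no score and "the particular visit will be excluded from the Rasch-transformed score calculation and summary". No rule covers a subject with no V7 questionnaire. SAP 8.3.4, the place for additional primary analyses, is marked not applicable.

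SAP 8.3.3 and the schedule place the questionnaire at screening and V7 only, so there is no intermediate score.

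The populations are as follows:
- **mITT** (SAP 4.1.1) is "all subjects who enrolled and had at least one post-baseline efficacy assessment at V7".
- **Evaluable** (SAP 4.1.2) requires mITT membership, receipt of both JUVÉDERM and BOTOX, at least one V7 efficacy assessment, and no significant deviation affecting efficacy.
- **Efficacy analyses** (SAP 8.1 and Appendix C) use the Evaluable Population alone.

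SAP 2.4 allows for the loss: "Anticipating a potential 20% drop-out rate (for early withdrawals and/or subjects who failed to duly complete" the primary questionnaire at end of study. That takes 48 analysable subjects to 60 enrolled.

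Protocol 6.2.6 and 11.1 and SAP 2.2 ask early discontinuers to attend the final visit. Protocol 8.2 adds that every effort should be made to obtain the primary questionnaire from them.

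**The concern.** The stated aim is to "quantify the psychological, social, and emotional impact of comprehensive aesthetic treatment with a portfolio of AbbVie's products". SAP 2.3 says "This is an open-label, single-arm study", so there is no control group and the size of the mean change is the main result. A mean taken over subjects who finished and answered describes a different group from those who started treatment.

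The two groups need not be alike. The discontinuation reasons in Protocol 8.2 include "AEs or SAEs that render the subject unable to continue study participation", withdrawn consent and inability to tolerate the treatment. Each could go with lower satisfaction. If those who leave gained less than those who stay, the reported mean is too high, and no planned output shows by how much.

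Subjects are lost from the primary mean by three routes:
1. **No V7 efficacy assessment of any kind.** The subject is in neither mITT nor Evaluable.
2. **Some V7 assessment (SPA, PAAQ or GAIS) but no computable FACE-Q score.** The subject can remain in both sets but adds nothing to the primary mean.
3. **Treatment stopped before BOTOX, which the schedule first gives at V5, and a return for V7 with a FACE-Q score.** The score exists, but the subject is outside Evaluable.

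**Working it through.** **Inputs from SAP 2.4.** Mean change 12.0, SD 25.0, 48 analysable, 60 enrolled, 20% loss. The test is as stated there: "This calculation is based on a one-sample, 1-sided t-test at 0.025 significance level".

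**Assumptions.** All 60 enrolled are treated. The mean change m among subjects without a usable score is not in the documents and is varied.

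**Step 1: the plan's own figures.** With noncentrality (12/25) × √48 and 47 degrees of freedom, power is 90.3%. With n = 47 it is 89.6%, so 48 is the smallest n that reaches 90%. Then 48 / (1 − 0.20) = 60. The plan's figures reproduce.

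**Step 2: size of the overstatement.** Let d be the share of treated subjects who do not contribute to the primary mean.

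All-treated mean = (1 − d) × 12 + d × m, so overstatement = 12 − that mean = d × (12 − m).

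| d | m (assumed) | All-treated mean | Overstatement | Share of 12 |
|---|---|---|---|---|
| 20% | 12 | 12.0 | 0 | 0% |
| 20% | 9 | 11.4 | 0.6 | 5% |
| 20% | 6 | 10.8 | 1.2 | 10% |
| 20% | 0 | 9.6 | 2.4 | 20% |
| 20% | −6 | 8.4 | 3.6 | 30% |
| 10% | 6 | 11.4 | 0.6 | 5% |
| 10% | 0 | 10.8 | 1.2 | 10% |

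**Step 3: effect on the test and the interval.**
- **Completers, n = 48:** SE = 25/√48 = 3.61, t = 12/3.61 = 3.33, lower 97.5% limit = 12 − 2.012 × 3.61 = 4.74.
- **Twelve zero changes added, n = 60:** mean = 48 × 12/60 = 9.6. Sum of squares = 47 × 625 + 48 × (12 − 9.6)² + 12 × (0 − 9.6)² = 29,375 + 276.5 + 1,105.9 = 30,757.4. SD = √(30,757.4/59) = 22.83, SE = 22.83/√60 = 2.95, t = 3.26, lower limit = 9.6 − 2.001 × 2.95 = 3.70.

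The t statistic barely moves (3.33 to 3.26). The estimate falls by 2.4 points and the lower limit by about 1 point. Part of the stability is artificial, because twelve identical zeros reduce the SD from 25 to 22.83. If the 12 instead have mean 0 and SD 25, the sum of squares gains 11 × 625 and becomes 37,632.4. The SD is then 25.26, t = 2.94 and the lower limit 3.08.

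**Step 4: tipping point.** Solving for the m at which the lower limit of the 60-subject analysis reaches 0 gives about −16 if the 12 share one constant change, and about −13 if their SD is 25.

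**The case against.** The best defence is that the loss is actively countered. Discontinuers are asked back, the primary questionnaire is singled out for retrieval, and the 20% is a planning allowance, not a forecast. Discontinuation reasons are tabulated (SAP 5.0), and FACE-Q is listed for the Safety Population (SAP 8.3.3), so the loss will be visible. This stands in part, since retrieval may bring d well below 20%. But a listing gives no estimate, and a returner who stopped before BOTOX is left out of the primary mean despite having a score.

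A second defence is that the conclusion is robust. The missing subjects would have to worsen by roughly 13 to 16 points before the lower limit reached zero, and a bias of 1.2 to 2.4 points is smaller than the completers' standard error of 3.61. This stands for the test. It does not settle the point, because sampling error is reported through the interval and this bias is not reported at all.

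Three stronger readings are tempting but not supported:
- **Everyone without a V7 FACE-Q score leaves every efficacy set.** Both definitions ask for any V7 efficacy assessment, so SPA, PAAQ or GAIS is enough to stay in mITT, and in Evaluable if its other conditions are met.
- **The plan overstates the effect by 10–20%.** That range needs the full 20% loss and m between 0 and 6. Neither is an observed fact, and the range starts at 0.
- **Restoring the mITT efficacy analysis would cure it.** It would recover returners who stopped before BOTOX, but not subjects with no V7 FACE-Q score.

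**Conclusion.** The gap is real. The protocol passed the missing-data strategy to the SAP, and the SAP covers missing items but not missing V7 scores. The primary result is the mean change among Evaluable subjects with a V7 score, and nothing planned shows how far that could lie from the mean in all treated subjects.

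On the plan's figures the overstatement runs from 0, if missing subjects resemble completers, to 2.4 points (20% of the assumed effect), if 20% are missing with no average change. It would be larger if they worsened. The size rests on two unknowns, the actual loss after retrieval and m. The direction is upward only if those lost gained less, which is plausible from the listed withdrawal reasons but is not shown by the documents. The significance test is not seriously at risk. What is affected is the estimate, its interval and the label put on them. A change to the SAP is worthwhile.

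**What to change.** Replace the not-applicable entry in SAP 8.3.4 with one supportive analysis of the primary endpoint:

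1. **Population:** all treated subjects with a baseline FACE-Q Satisfaction score.
2. **Observed data:** use every FACE-Q score collected at the end-of-study or early-discontinuation visit, whatever products the subject received.
3. **Missing scores:** multiple imputation with a delta-adjusted range that includes a mean change of zero, with the variance carried through to the interval. A fixed zero for each missing subject should not stand alone, because it understates the variance.
4. **Tipping point:** report the mean change among missing subjects at which the lower limit reaches 0.
5. **Reporting:** give the number of missing V7 scores and the reasons, and label the main result as the change among Evaluable subjects with a V7 score.

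The cost is SAP wording and one extra table. No new data, visits or subjects are needed. The downside is that the supportive mean may be less favourable than the main one.
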